APPENDIX D. MSPLINE VALUE FOR CALCULATION OF PREDICTED SVC57

LIST OF TABLES

Table 1: CY 5022 Randomized, Double-Blind Treatment Groups15
Table 2: Analysis Set and Summary Level.....19
Table 3: Dimensions and Items of ALSAQ-5.....26
Table 4: Interpretation of Score Ranges for Dimensions on ALSAQ-527
Table 5: Depression Level Classification by BDI Total Score.....29
Table 6: Criteria of Potentially Clinically Significant (PCS) Vital Signs42
Table 7: Criteria of Abnormal and PCS ECG Values.....43

LIST OF FIGURES

Figure 1: Patient Visit Diagram16

LIST OF ABBREVIATIONS

The following abbreviations are used in this analysis plan.

Abbreviation	Term
AE	adverse event
ALSAQ-5	ALS Assessment Questionnaire Short Form
ALS	amyotrophic lateral sclerosis
ALSFRS-R	ALS Functional Rating Scale - Revised
ALT	alanine aminotransferase (alanine transaminase)
AST	aspartate aminotransferase (aspartate transaminase)
AUC	area under the plasma concentration-time curve
BDI	Beck Depression Inventory
BMI	body mass index
CI	confidence interval
C _{max}	maximum observed plasma concentration
C _{trough}	pre-dose plasma concentration
CTCAE	Common Terminology Criteria for Adverse Events
CV	coefficient of variation
DMC	Data Monitoring Committee
ECG	electrocardiogram
eCRF	electronic case report form
eGFR	estimated glomerular filtration rate
FAS	full analysis set
HHD	hand-held dynamometry
ICF	informed consent form
LLOQ	lower limit of quantitation
MedDRA	Medical Dictionary for Regulatory Activities
MMRM	mixed model for repeated measures
NCI	National Cancer Institute
PCS	potentially clinically significant
PD	pharmacodynamic
PK	pharmacokinetic
PKS	pharmacokinetics analysis set
QTc	corrected QT interval
SAE	serious adverse event
SAS	safety analysis set
SD	standard deviation
SUSAR	suspected unexpected serious adverse reaction
SVC	slow vital capacity
TDD	total daily dose
TEAE	treatment emergent adverse event
t _{max}	time where maximum concentration is reached
ULN	upper limit of normal

1. INTRODUCTION

The purpose of this statistical analysis plan (SAP) is to provide a technical elaboration of the planned analyses and detailed data displays to be included in the Clinical Study Report (CSR) for CY 5022.

This SAP was developed in accordance with ICH E9 guideline. All decisions regarding final analysis, as defined in this SAP document, will be made prior to the database lock (unblinding) of the study data. Further study information can be found in the protocol.

2. STUDY OBJECTIVES AND ENDPOINTS

2.1. Study Objectives

2.1.1. Primary Objective

The primary objective of this study is to assess the effect of reldesemtiv versus placebo on respiratory function in patients with amyotrophic lateral sclerosis (ALS).

2.1.2. Secondary Objectives

The secondary objectives of this study are:

- To assess the effect of reldesemtiv versus placebo on measures of skeletal muscle function
- To assess the effect of reldesemtiv versus placebo on global function
- To evaluate the safety and tolerability of reldesemtiv administered orally to patients with ALS
- To evaluate the exposure of reldesemtiv and its metabolites, when administered orally in tablet form to patients with ALS in the fed state

2.1.3. Exploratory Objectives

The exploratory objectives of this study are:

- To assess the effect of reldesemtiv versus placebo on respiratory function self-assessments made at home by patients with help as needed by caregivers
- To assess the effect of reldesemtiv versus placebo on disease progression through measurement of speech production characteristics over time
- To assess the effect of reldesemtiv versus placebo on disease progression through measurement of handwriting abilities over time
- To assess the change from baseline to Visit Week 12 in quality of life (as measured by the ALS Assessment Questionnaire Short Form [ALSAQ-5]) and muscle strength in patients on reldesemtiv compared to placebo

- To assess the change in the slope of decline of measures of function in patients on reldesemtiv compared to placebo

2.1.4. Pharmacokinetic / Pharmacodynamic Objectives

The pharmacokinetic (PK) / pharmacodynamic (PD) objectives of this study are to characterize the pharmacokinetics of reldesemtiv following multiple doses in the fed state at three dose levels in ALS patients as well as to evaluate possible relationships between both dose and exposure of reldesemtiv and its pharmacodynamic effects following multiple oral doses in patients with ALS.

2.2. Study Endpoints

2.2.1. Efficacy Endpoints

2.2.2. Primary Efficacy Endpoint

The primary efficacy endpoint is the change from baseline to Visit Week 12 in percent predicted slow vital capacity (SVC).

2.2.3. Secondary Efficacy Endpoints

- Slope from baseline to Visit Week 12 in the muscle strength mega score measured by hand held dynamometry (HHD) and handgrip dynamometry
- Change from baseline to Visit Week 12 in the ALS Functional Rating Scale – Revised (ALSFRS-R)

2.2.4. Exploratory Efficacy Endpoints

Endpoints assessed as a change from baseline include:

- Change from baseline to Visit Week 12 in the percent predicted SVC measured at home
- Change from baseline to Visit Week 12 in the components of voice analysis
- Change from baseline to Visit Week 12 in the components of handwriting analysis
- Percent change in the strength of the muscle groups from baseline to Visit Week 12 that contribute to the Mega score at Visit Week 12
- Change from baseline to Visit Week 12 in the ALSAQ-5

Endpoints assessed as a change in slope include:

- Slope of change from baseline to Visit Week 12 in the percent predicted SVC
- Slope of change from baseline to Visit Week 12 in the ALSFRS-R
- Slope of change from baseline to Visit Week 12 in percent predicted SVC measured at home
- Slope of change from baseline to Visit Week 12 in the components of voice analysis

- Slope of change from baseline to Visit Week 12 in the components of handwriting analysis
- Slope of change from baseline to Visit Week 12 in the ALSAQ-5

2.2.5. Safety Endpoints

The safety endpoints are listed in the following:

- Incidence and severity of treatment-emergent adverse events (TEAEs)
- Clinically important changes in safety assessment results [including, as appropriate, vital signs, clinical laboratory tests, ECGs, Ashworth score, falls assessment, physical and neurological examinations, beck depression inventory and suicidality assessment]

2.2.6. Pharmacokinetic Measurements

- The plasma concentrations of reldesemtiv and possible metabolites will be measured at the sampled time points during the study.

3. STUDY DESIGN

3.1. Summary of Study Design

[figure not shown]
This is a Phase 2, double-blind, randomized, placebo-controlled, dose ranging study of reldesemtiv in patients with ALS. An overview of the randomized treatment groups is provided in [Table 1](#):

Table 1: CY 5022 Randomized, Double-Blind Treatment Groups

CK-2127107			Placebo
300 mg TDD 1 tablet (150 mg) of reldesemtiv and 2 placebo tablets twice daily for 12 weeks	600 mg TDD 2 tablets (150 mg) of reldesemtiv and 1 placebo tablet twice daily for 12 weeks	900 mg TDD 3 tablets (150 mg) of reldesemtiv twice daily for 12 weeks	3 placebo tablets twice daily for 12 weeks

The screening and qualification period for the study will be no more than 14 days in duration. Once patients have completed screening and are considered eligible for the study, they will be randomized as described above and stratified by riluzole and edaravone use status.

Figure 1: Patient Visit Diagram

PD measures, vital signs, ECGs, and clinical laboratory evaluations will be performed at Screening and at specified times during the study. Patients will be evaluated at each study visit for signs and symptoms of intolerance to study drug.

3.2. Description of Study Drug

Reldesemtiv is a small molecule activator of the fast skeletal muscle troponin complex, a sarcomere-directed therapy intended to improve skeletal muscle function in conditions associated with muscle weakness and/or fatigue. Reldesemtiv is supplied as immediate release, white to off-white, modified capsule-shaped tablets. Active reldesemtiv tablets contain 150 mg of reldesemtiv per tablet plus excipients. Placebo tablets contain excipients only. Reldesemtiv and matching placebo tablets will be supplied to the clinical site in blister strips inside labeled wallets. Patients will receive one or more wallets of study drug, reldesemtiv or matching placebo at the appropriate visit. Each wallet is sufficient for one week of dosing, plus overage. Double-blind wallets will be labeled with a unique random kit number.

3.3. Sample Size Consideration

3.3.1. Sample Size Justification

Approximately 445 patients will be randomized. The dropout rate at Visit Week 12 is estimated to be 10%, thus approximately 400 patients are expected to complete 12 weeks of double-blind treatment. The effect of reldesemtiv on the change from baseline to Week 12 in percent predicted SVC will be analyzed using a mixed model for repeated measures (MMRM) with the contrast (-5, -1, 3, 3) to reflect the assumed relationship for the placebo, 300 mg/day, 600 mg/day and 900 mg/day dose groups. The sample size is estimated to provide 90% power to detect 2.75, 5.5 and 5.5 percentage points advantage over placebo in the change from baseline to Visit Week 12 of

percent predicted SVC for the 300 mg/day, 600 mg/day and 900 mg/day reldesemtiv dose groups, respectively. This calculation is based on a two-sided test with alpha set at 0.05 and a common standard deviation (SD) of 14 percentage points.

3.4. Randomization

Patients will be randomized to receive either one of the three reldesemtiv doses (300 mg/day, 600 mg/day and 900 mg/day TDD) or matching placebo tablets in a ratio of 1:1:1:1. Randomization will be stratified by riluzole and edaravone use status at baseline.

3.5. Clinical Assessments

Clinical assessments of all visits are listed in Schedule of Events in [Appendix A](#).

4. PLANNED ANALYSES

4.1. Safety Monitoring

An independent data monitoring committee (DMC) will meet after approximately 30% of patients complete 2 weeks of dosing to review the accumulated safety data (potentially unblinded) for this trial. This committee will make a recommendation as to the continuation of this study based on safety data analysis reports provided at the meeting. The DMC will also provide recommendation(s) on the study conduct.

The DMC will be informed of all initial suspected unexpected serious adverse reactions (SUSARs) within 15 days from the time Cytokinetics is first made aware of it. The DMC will further receive the final case versions of all SUSARs within 15 days after the case closure. DMC will also receive monthly summaries and listings of all serious adverse events and early termination of study treatment.

The DMC may review additional data for safety monitoring purpose. The DMC or Cytokinetics can require an ad hoc DMC meeting at any time. No study activities will be suspended during the safety review.

4.2. Interim Analyses

Not applicable.

4.3. Final Analyses

The final analysis will be conducted after all patients have either completed all the scheduled study visits or have early terminated from the study. At that time, the database will be cleaned and locked and the study treatment will be unblinded. All endpoints will be analyzed based on the final data after the database is locked.

5. GENERAL CONSIDERATIONS FOR DATA ANALYSES AND HANDLING

5.1. General Summary Table and Individual Patient Data Listing Considerations

Summary tables will present descriptive statistics such as number of patients, mean, median, standard deviation, minimum and maximum for continuous variables, and number of patients and the percentage for categorical variables, by dose level in the planned analysis sets. For model based analysis, least square mean, difference of least square means among various dose levels, their standard errors and 95% confidence intervals, and two-sided p-values for the relative statistical inferences will be presented. For survival analyses, time to event will be summarized by median, 95% CI of median, and 1st and 3rd quartiles. Number and percentage will be presented for patients with events and patients whose data are censored. Hazard ratio between dose levels and the corresponding 95% CI and p-value will also be presented.

Listings will include patient ID, demographics, dose level assigned and other relevant items, and sorted by treatment assignment, patient ID and date of assessment.

5.2. Data Management

Data will be entered into the clinical database with programmed edit checks and manual data review to insure integrity. Adverse events, Concomitant Medications and Medical History will be coded automatically by imbedded program in the clinical database with manual review of unique terms. Clinical safety laboratory, pharmacokinetic, handwriting, and voice recording data will be provided from external laboratory(s) or research organization(s) in the pre-specified format.

5.3. Data Presentation Conventions

The following conventions are applied to all data presentations and summaries.

- For continuous variables, all mean and median values are formatted to one more decimal place than the measured value. Standard deviation values are formatted to two more decimal places than the measured value. Minimum and maximum values are presented with the same number of decimal places as the measured value.
- For categorical variables, the number and percentage of responses are presented in the form XX (XX.X%) where the percentage is in the parentheses.
- Date variables are formatted as DDMMYY for presentation. Time is formatted in military time as HH:MM for presentation.
- P-values, if applicable, will be presented to 4 decimal places. If the p-value is less than 0.0001 then it will be presented as <0.0001. If the rounded result is a value of 1.000, it will be displayed as >0.9999.
- Unless otherwise stated, any statistical tests performed will use 2-sided tests at the 5% significance level.

The table, figure and listing shells and table of contents provide the expected layout and titles of the produced outputs of tables, figures and listings. Only differences in the analysis methods or data handling will necessitate a SAP revision.

5.4. Analysis Sets

5.4.1. Full Analysis Set

The Full Analysis Set (FAS) will consist of all randomized patients who received any amount of study drug and have a baseline and at least one post baseline efficacy assessment during the double-blind treatment.

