5.15. Removal of Patients from Study Participation

Patients will be informed that they are free to discontinue study drug or withdraw from the study at any time and for any reason. The Investigator may discontinue study drug or withdraw a patient from the study if, in the Investigator's opinion, it is not in the best interest of the patient to continue the study. Patients may discontinue study drug or withdraw from the study due to the following:

- a. A change in compliance with inclusion/exclusion criteria that is clinically relevant and/or affects patient safety, and/or study assessments/objectives, etc.
- b. Occurrence of intolerable AEs
- c. Changes in vital signs, ECGs, or clinical laboratory results that, in the opinion of the Investigator, pose a significant health risk
- d. Intake of non-permitted concomitant medication that might affect patient safety or study assessments/objectives, etc.

- e. eGFR calculated using the CKD-EPI cystatin equation (Inker, Schmid et al. 2012) shows a >25% decline compared to baseline (defined as Day 1 or Screening if Day 1 value is not available) as long as the decline is not related to dehydration or a superimposed reversible process such as infection or nausea.
- f. Changes in liver function tests (LFTs) as outlined in [Appendix C](#)
- g. Receiving any form of stem cell therapy for ALS either as part of a clinical trial or outside of a clinical trial
- h. Having a diaphragmatic pacing system implanted either as part of a clinical trial or outside of a clinical trial
- i. Initiating edaravone after screening.
- j. Initiating riluzole after screening.
- k. Initiating gene therapy for ALS either as part of a clinical trial or outside of a clinical trial after screening.

Patients should be strongly encouraged to perform the early termination visit as soon as possible following last dose of study drug taken, and the Follow-Up Visit should be performed 28 days after last dose taken of study medication. In addition, they should be encouraged to return for all remaining study visits and assessments (with the exception of 12-lead ECG, clinical laboratory and PK sampling) for the duration of the study following study drug discontinuation. These remaining study visits should be performed according to the original study visit windows.

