8.2. Analysis Sets

8.2.1. Full Analysis Set (FAS)

The FAS will consist of all randomized patients who receive at least one dose or portion of a dose of study drug and who have a baseline and at least one post-baseline efficacy assessment during the double-blind treatment.

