5.4.4. Use of Analysis Sets in Different Analyses and Summary Level

The analysis datasets to be used are described in [Table 2](#).

Table 2: Analysis Set and Summary Level

Analyses	Analysis Set
Patients Disposition (Section 6.1)	Randomized Patients, FAS
Study Population (Section 6) except for Patients Disposition (Section 6.1) and Screen Failures (Section 6.2)	SAS, FAS
Efficacy Analyses (Section 7)	FAS
Safety and Tolerability (Section 8)	SAS
PK/PD Analyses (Section 9)	PKS

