7.5. Analysis of the Primary Efficacy Endpoints

7.5.1. Primary Efficacy Analysis

The primary efficacy endpoint (change from baseline to Visit Week 12 in percent predicted SVC) will be analyzed for the FAS based on the percent predicted SVCs collected in clinic and were confirmed evaluable by the central read of an independent pulmonologist. A MMRM with the contrast (-5, -1, 3, 3) will be used for the analysis to reflect the assumed relationship for the placebo, 300 mg/day, 600 mg/day and 900 mg/day dose groups. The response variable will be the change from baseline to each post baseline visit up to Week 12. The model will include the following covariates:

- Treatment (reldesemtiv 300 mg/day, 600 mg/day and 900 mg/day, and placebo)
- Baseline (baseline value of the response variable)
- Pooled site (Center)
- Visit (scheduled, a categorical variable)
- Riluzole and edaravone use status at baseline
- Treatment-by-visit interaction
- Baseline-by-visit interaction

An unstructured variance-covariance structure will be used to model the within-subject errors. If a model fails to converge, other covariance matrix structures (eg, compound symmetry) may be used instead of the unstructured covariance matrix. Least square means and the corresponding standard errors, 95% CIs and p-values will be presented.

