7.5.2. Sensitivity Analyses of the Primary Efficacy Results

Sensitivity analysis under the assumption of missing not at random (MNAR) will be conducted using control-based pattern imputation approach ([Ratitch 2011](#)) for the primary efficacy endpoint (change from baseline to Visit Week 12 in percent predicted SVC). A model for imputing missing observations of percent predicted SVC in both reldesemtiv and placebo groups will be constructed using the observed data in the placebo group. The sensitivity analysis will include all observed and the aforementioned imputed data in the analysis model for the primary efficacy endpoint.

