7.9. Exploratory Analyses

7.9.1. Joint Rank Test

Joint rank analyses using the combined assessment of function and survival (CAFS) ([Berry 2013](#)) will be conducted to account for survival time in the analyses of change in the percent predicted SVC and ALSFRS-R total score at Week 12, individually.

Each patient will be compared with all others in the analysis population in a pairwise manner on their survival status and the functional measurements, ie, changes from baseline in the percent predicted SVC or ALSFRS-R total score. A score of +1 or -1 will be assigned if one has better or worse outcome than the other, respectively. The following rule will be used:

- Patients who died are ranked worse than those who survived.
- Among patients who died, patients who died first are ranked worse.
- For patients who discontinued treatment early but were alive, comparison is based on the last time-point measurements that are both available for the patients in pairs. A patient is ranked worse if the patient discontinued treatment early and did not have functional measurement collected before the discontinuation.
- Among patients who completed, patients with greater decline from baseline in the functional measurement are ranked worse.
- If it is not possible to assign either patient as having the better outcome, then the score assigned to the pair is 0.

For each patient, the assigned scores from the pairwise comparisons with all others will first be summed, and all patients in the analysis population will be ranked according to their summated scores to create a rank score from 1 for the lowest summated score to N (total number of patients in the analysis population) for the highest summated score. If ties occur, each of the tied summated scores will be assigned the average of the ranks the tied summated scores would have if there were no ties.

The rank scores will be analyzed using the generalized Gehan-Wilcoxon test. In addition, the rank scores will be analyzed using an ANCOVA model that adjusts for baseline variables (baseline functional measurement, time from symptom onset, site of disease onset and riluzole or edaravone use). The rank scores between the reldesemtiv and placebo groups will be compared, and the least square mean difference as well as the p-value will be presented.

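### Treated patients who die or leave before any post-baseline efficacy assessment fall outside the FAS, so the control-based imputation and the joint rank test never count them

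*SAP*

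**What the plan says.** The restriction is in both documents. SAP 5.4.1 requires that FAS patients "have a baseline and at least one post baseline efficacy assessment during the double-blind treatment". Protocol 8.2.1 takes randomised, dosed patients "who have a baseline and at least one post-baseline efficacy assessment during the double-blind treatment". Neither document says whether the last clause means while taking study drug or during the 12-week period.

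SAP Table 2 (5.4.4) assigns the FAS to the row beginning "Efficacy Analyses (Section 7". That row covers three analyses:

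- The primary (SAP 7.5.1) "will be analyzed for the FAS based on the percent predicted SVCs collected in clinic", using only values confirmed by the central read.
- The control-based sensitivity analysis (SAP 7.5.2) uses "A model for imputing missing observations of percent predicted SVC in both reldesemtiv and placebo groups", built from observed placebo data. It names no other analysis set.
- The joint rank test (SAP 7.9.1) speaks only of the analysis population. Its rules include "Patients who died are ranked worse than those who survived" and "A patient is ranked worse if the patient discontinued treatment early and did not have functional measurement collected before the discontinuation".

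On follow-up after stopping drug, Protocol 5.15 says of patients that "they should be encouraged to return for all remaining study visits and assessments". Protocol 5.8 describes an early termination visit with SVC, muscle strength and ALSFRS-R. SAP 5.5.4 and Appendix B assign early-discontinuation records to analysis windows by study day, and Days 2 to 21 go to Week 2.

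**The concern.** Being in the FAS depends on something that happens after randomisation. Usually that costs little. Here it bears on the two analyses whose purpose is to show what dropout and death do to the result. The control-based imputation is meant to give missing active patients a placebo-like course, but it gives nothing to a patient who left before any efficacy record existed. The joint rank test is meant to bring survival into the comparison, but a treated patient who dies before a first post-baseline assessment receives no rank.

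The undefined clause is a second problem. Read as on drug, it removes a patient who stops in the first days and then attends Weeks 2 to 12 off drug. A patient with the same off-drug visits who had one assessment before stopping stays in. The protocol asks for those visits and the SAP windows the data, so their use should not rest on an unwritten choice.

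**Working it through.** **1. Who is in the FAS.** Consider treated patients with a baseline who stop or die before the first scheduled post-baseline clinic visit (Week 2, Day 15).

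| Post-baseline efficacy records | Clause means on drug | Clause means the 12-week period |
|---|---|---|
| None at all | out | out |
| A home SVC or voice record made before stopping | in | in |
| Only off-drug records (early termination visit, telephone ALSFRS-R, later visits) | out | in |

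The first row is left out on either reading. These patients are absent from 7.5.2 and 7.9.1. Their absence from the primary MMRM is not caused by the FAS: with no post-baseline clinic SVC they supply no response in any analysis set. The third row reaches the primary, but only on the on-drug reading.

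**2. The plan's own figure.** Inputs from Protocol 8.1.2: contrast (-5, -1, 3, 3); advantages over placebo 2.75, 5.5 and 5.5; SD 14; about 400 completers, so 100 per arm; two-sided 0.05.

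- Contrast value: -2.75 + 3 × 5.5 + 3 × 5.5 = 30.25
- SE: 14 × √((25 + 1 + 9 + 9)/100) = 14 × √0.44 = 9.287
- z = 30.25/9.287 = 3.257; power = Φ(3.257 - 1.960) = 0.903, which reproduces the stated 90%
- N: 400/0.9 = 444.4, rounded up to 445, as stated

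Divided by 6, as in the SAP Section 13 code, the contrast is 30.25/6 = 5.04 points with SE 9.287/6 = 1.55.

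**3. Number affected.** The site counts in SAP Appendix C sum to 458 FAS patients: 20 + 53 + 49 + 52 + 61 + 71 + 51 + 36 + 65. The number randomised or dosed is not given, so the number excluded cannot be derived. What follows are illustrations under assumptions.

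**4. Control-based imputation.** Assume 10% of each active arm is missing at Week 12 (the planned dropout) and imputed as placebo. Let a fraction e of the arm be early exits that the FAS removes. The missing share left in the FAS is f = (0.10 - e)/(1 - e). The 600 and 900 mg effect is 5.5 × (1 - f), and the scaled contrast is 5.04 × (1 - f).

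| e | f | 600/900 mg effect | Scaled contrast |
|---|---|---|---|
| 0 | 0.100 | 4.95 | 4.54 |
| 1% | 0.091 | 5.00 | 4.58 |
| 2% | 0.082 | 5.05 | 4.63 |
| 3% | 0.072 | 5.10 | 4.68 |
| 5% | 0.053 | 5.21 | 4.78 |

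With 445/4 ≈ 111 per arm, 1-5% is about 1 to 6 patients. Leaving them out makes the 600/900 mg estimate 0.05 to 0.26 points less conservative. On the scaled contrast the shift is about 0.05 to 0.24, or 3% to 15% of the 1.55 SE.

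**5. Joint rank test.** A simplified simulation used 111 placebo against 222 pooled 600/900 mg patients, normal outcomes with SD 14, 4,000 runs and a Wilcoxon-Mann-Whitney test. Early exits were ranked worst and there was no other dropout.

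| Exits, placebo / active | True effect | Rejection rate, exits ranked | Rejection rate, exits excluded |
|---|---|---|---|
| 1% / 1% | 5.5 | 0.90 | 0.91 |
| 1% / 3% | 5.5 | 0.81 | 0.90 |
| 1% / 5% | 5.5 | 0.70 | 0.91 |
| 1% / 5% | 0 | 0.09 | 0.05 |

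Balanced exits barely matter. Imbalanced exits do, and excluding them hides the imbalance the test is there to register.

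**The case against.** The definition is looser than it first looks. It asks for any efficacy assessment, not a clinic SVC. Weekly home SVC and voice recordings begin after Day 1 and both are listed efficacy endpoints. Protocol 8.1.2 treats the end of double-blind treatment as another name for Visit Week 12, which favours the 12-week reading. So does the rank rule for patients with no measurement before stopping, which has more patients to act on if off-drug records admit them to the FAS. The affected analyses are supportive: 7.5.2 is a sensitivity analysis and 7.9.1 is exploratory, both outside the testing hierarchy in SAP 7.4. Deaths are summarised on the Safety Analysis Set, and SAP 7.8 lists reasons for FAS exclusion, so an imbalance would be visible.

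Most of this stands, and it limits the point. A reader might infer that everyone who stops before Week 2 leaves the primary analysis. The documents do not support that, for the reasons in step 1 of the working.

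The home records are only a partial rescue. They depend on a device suitable for the region or access to a mobile device, and SAP 7.9.3 reports that spirometer use varies among patients. None of these arguments reaches the patient with no post-baseline record, and a listing of exclusions does not replace imputing or ranking that patient.

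**Conclusion.** The point holds in a limited form. On either reading, a treated patient who dies or leaves before any post-baseline efficacy assessment is outside the control-based imputation and the joint rank test, and the rank rules are written as if such patients were present. The primary is affected only on the on-drug reading, through patients whose sole post-baseline data are off drug.

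The effect is probably small: about 0.05-0.26 points on a 5.5-point effect if 1-5% of an active arm are such exits. That range is an assumption. Its upper end would put half of the planned 10% dropout into this group. The joint rank result changes materially only if exits differ by arm, and the documents give no evidence that they do.

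Two further inferences are tempting and should not be drawn:

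- *That the shift always favours the arm with more early stops.* Under the placebo-like assumption, removing active exits raises the estimate even when rates are equal, and removing placebo exits changes nothing. Under other assumptions about unseen outcomes the direction can reverse.
- *That Phase 1 shows dose-related early stopping.* Protocol 1.3 reports dizziness, headache and nausea rising at 2250 mg and above, with no severe events and no discontinuations for adverse events. The highest dose here is 450 mg twice daily.

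This is a cheap improvement, not a threat to the primary conclusion.

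**What to change.** 1. Run SAP 7.5.2 and 7.9.1 on all randomised patients who took any study drug. That set already exists as the Safety Analysis Set (SAP 5.4.2). Where there is no post-baseline value, impute from baseline in 7.5.2, and rank on survival and discontinuation in 7.9.1. Name the set in both sections and in Table 2.
2. State in SAP 5.4.1 that the double-blind treatment clause means up to Week 12, on or off study drug.
3. Record both changes in SAP Section 12, which at present lists none. Protocol 8.2.1 has the same FAS wording and Protocol 8.4.4 places efficacy analyses on the FAS. Protocol 8.7 provides for reporting such changes in the study report.

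No new data are needed. The costs are wording, a second analysis set to report, and slightly more conservative supportive results. If item 2 changes who is in the FAS, the counts in Appendix C need rechecking. All of this should be settled before database lock.
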